10.6 Day 5 Treatment

1. Record vital signs, oxygen requirements, and physical examination findings.
2. Concomitant medications review
3. Review medical records to record data for endpoints.
4. Administer study drugs to participants according to randomization
5. Review and record any Adverse Events.
6. Collect blood for clinical laboratory tests (can be used for clinical care)
 - a. 1x citrate tube
 - b. 1x SST tube
 - c. 1x EDTA tube
7. Collect blood for research laboratory tests on Day 5 (\pm 1 day)
 - a. 5x citrate tubes
 - b. 1x SST tube
 - c. 1x PAXgene RNA tube

10.7 Day 6 Treatment

1. Record vital signs, oxygen requirements, and physical examination findings.
2. Concomitant medications review
3. Review medical records to record data for endpoints.
4. Administer study drugs to participants according to randomization
5. Review and record any Adverse Events.

10.8 Day 7 Treatment

1. Record vital signs, oxygen requirements, and physical examination findings.
2. Concomitant medications review

3. Review medical records to record data for endpoints.
4. Administer study drugs to participants according to randomization
5. Review and record any Adverse Events.
6. Collect blood for clinical laboratory tests (can be used for clinical care)
 - a. 1x citrate tube
 - b. 1x EDTA tube
7. Collect blood for research laboratory tests on Day 7 (\pm 1 day)
 - a. 1x citrate tube
 - b. 1x SST tube

10.9 Day 8 Treatment

1. Record vital signs, oxygen requirements, and physical examination findings.
2. Concomitant medications review
3. Review medical records to record data for endpoints.
4. Administer study drugs to participants according to randomization
5. Review and record any Adverse Events.

10.10 Day 9 Treatment

1. Record vital signs, oxygen requirements, and physical examination findings.
2. Concomitant medications review
3. Review medical records to record data for endpoints.
4. Administer study drugs to participants according to randomization
5. Review and record any Adverse Events.
6. Collect blood for clinical laboratory tests (can be used for clinical care)
 - a. 1x citrate tube
 - b. 1x SST tube
 - c. 1x EDTA tube
7. Collect blood for research laboratory tests on Day 9 (\pm 1 day)
 - a. 1x citrate tube
 - b. 1x SST tube
 - c. 1x EDTA tube

10.11 Day 10 Treatment

1. Record vital signs, oxygen requirements, and physical examination findings.
2. Concomitant medications review
3. Review medical records to record data for endpoints.
4. Administer study drugs to participants according to randomization
5. Review and record any Adverse Events.

10.12 Day 11 Treatment

1. Record vital signs, oxygen requirements, and physical examination findings.
2. Concomitant medications review

3. Review medical records to record data for endpoints.
4. Administer study drugs to participants according to randomization
5. Review and record any Adverse Events.
6. Collect blood for clinical laboratory tests (can be used for clinical care)
 - a. 1x citrate tube
 - b. 1x EDTA tube
7. Collect blood for research laboratory tests on Day 11 (\pm 1 day)
 - a. 1x citrate tube
 - b. 1x SST tube

10.13 Day 12 Treatment

1. Record vital signs, oxygen requirements, and physical examination findings.
2. Concomitant medications review
3. Review medical records to record data for endpoints.
4. Administer study drugs to participants assigned to study drug arms.
5. Review and record any Adverse Events.
6. Administer study drugs to participants according to randomization
7. Collect blood for clinical laboratory tests

10.14 Day 13 Treatment

1. Record vital signs, oxygen requirements, and physical examination findings.
2. Concomitant medications review
3. Review medical records to record data for endpoints.
4. Administer study drugs to participants according to randomization
5. Review and record any Adverse Events.
6. Collect blood for clinical laboratory tests (can be used for clinical care)
 - a. 1x citrate tube
 - b. 1x SST tube
 - c. 1x EDTA tube
7. Collect blood for research laboratory tests on Day 13 (\pm 1 day)
 - a. 1x citrate tube
 - b. 1x SST tube

10.15 Day 14 Treatment

1. Record vital signs, oxygen requirements, and physical examination findings.
2. Concomitant medications review
3. Review medical records to record data for endpoints.
4. Administer study drugs to participants according to randomization
5. Review and record any Adverse Events.
6. Collect blood for clinical laboratory tests (can be used for clinical care)
 - a. 1x citrate tube

- b. 1x EDTA tube

10.16 Early Withdrawal Interaction

1. Record vital signs, oxygen requirements, and physical examination findings.
2. Review medical records to record data for endpoints
3. Concomitant medications review.
4. Review and record any Adverse Events.
5. Collect blood for clinical laboratory tests as described in the informed consent document.
 - a. 1x citrate tubes
 - b. 1x SST tube
 - c. 1x EDTA tube
6. Collect blood for research laboratory tests as described in the informed consent document.
 - a. 1x citrate tubes
 - b. 1x SST tube
7. Follow up call to participant for adverse events, 30 days after last dose of study drug

10.17 30 Days after last dose of study drug (\pm 2 day)

Chart review and follow up call to participant for AEs assessment up to 30 days after last dose of study drug (maximum of 44 days from initiation of trial participation).

11 ADVERSE EXPERIENCE REPORTING AND DOCUMENTATION

11.1 Adverse Events

An adverse event (AE) is any untoward medical occurrence in a clinical investigation of a participant administered a pharmaceutical product and that does not necessarily have a causal relationship with the treatment. An AE is therefore any unfavorable and unintended sign (including an abnormal laboratory finding), symptom or disease temporally associated with the administration of an investigational product, whether or not related to that investigational product. An unexpected AE is one of a type not identified in nature, severity, or frequency in the current protocol or of greater severity or frequency than expected based on the information in the protocol.

The Investigator or designee will probe, via medical record review, for the occurrence of AEs during each study day for the duration of study drug administration, and record the information in the source documents. Adverse events will be described by duration (start and stop dates and times), severity, outcome, treatment and relation to study drug, or if unrelated, the cause.

11.2 AE Severity

The guidelines shown in below [Table 2](#) should be used to grade severity. It should be pointed out that the term “severe” is a measure of intensity and that a severe AE is not necessarily serious.

Table 2: AE Severity Grading

Severity (Toxicity Grade)	Description
Mild (1)	Transient or mild discomfort; no limitation in activity; no medical intervention or therapy required. The participant may be aware of the sign or symptom but tolerates it reasonably well.
Moderate (2)	Mild to moderate limitation in activity, no or minimal medical intervention/therapy required.
Severe (3)	Marked limitation in activity, medical intervention/therapy required, hospitalizations possible.
Life-threatening (4)	The participant is at risk of death due to the adverse experience as it occurred. This does not refer to an experience that hypothetically might have caused death if it were more severe.

11.2.1 AE Relationship to Study Drug

The relationship of an AE to the study drug will be assessed using the following the guidelines.

Table 3: AE Relationship to Study Drug

Relationship to Drug	Comment
Definitely	Previously known toxicity of agent; or an event that follows a reasonable temporal sequence from administration of the drug; that follows a known or expected response pattern to the suspected drug; that is confirmed by stopping or reducing the dosage of the drug; and that is not explained by any other reasonable hypothesis.
Probably	An event that follows a reasonable temporal sequence from administration of the drug; that follows a known or expected response pattern to the suspected drug; that is confirmed by stopping or reducing the dosage of the drug; and that is unlikely to be explained by the known characteristics of the participant’s clinical state or by other interventions.
Possibly	An event that follows a reasonable temporal sequence from administration of the drug; that follows a known or expected response pattern to that suspected drug; but that could readily have been produced by a number of other factors.
Unrelated	An event that can be determined with certainty to have no relationship to the study drug.

11.2.2 *Serious Adverse Experiences (SAE)*

An SAE is defined as any AE occurring at any dose that results in any of the following outcomes: major bleeding as defined by ISTH, AST or ALT > 10 times the upper limit of normal.

Other important medical events may also be considered a SAE when, based on appropriate medical judgement, they jeopardize the participant or require intervention to prevent one of the outcomes listed.

11.2.3 *Serious Adverse Experience Reporting*

Study personnel will document all SAEs that occur (whether or not related to study drug). The collection period for all SAEs will begin after informed consent is obtained and end 30 days after administration of the last dose of study drug.

In accordance with the standard operating procedures and policies of the local IRB, the study team will report SAEs to the IRB.

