3.3 Safety Outcomes

1. **Title:** Incidence of serious adverse events
Description: Incidence of serious adverse events as defined in the study protocol.
Time Frame: Data gathered through 30 days after administration of last drug dose
2. **Title:** Incidence of severe hypotension
Description: Hypotension with systolic blood pressure < 90 mmHg requiring more than a 1-L IV fluid bolus
Time Frame: Data gathered through day 14 ± 1 day
3. **Title:** Incidence of major bleeding
Description: Incidence of major bleeding defined in accordance with the criteria of the International Society on Thrombosis and Hemostasis (ISTH) as bleeding that is associated with a decrease in the hemoglobin level of 2 g per deciliter or more, leads to a transfusion of 2 or more units of blood, occurs in a critical site, or contributed to death
Time Frame: Data gathered through day 28 ± 1 day

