8.6 Interim Analyses and Data Monitoring

8.6.1 Safety Review

The analysis plan includes interim review by the DSMB for the purpose of monitoring study conduct and assessing participant safety after 50% of patients have completed the study or 10 deaths have occurred (whichever happens first). This review includes the number, proportion, and listing of participants with SAEs (including segregation of those involving deaths), treatment-emergent AEs, and discontinuation of study medication due to AEs. These presentations are descriptive, with no formal inferential methods used. No specific rules for halting study enrollment or study interventions for safety are specified; however, the DSMB may request formal inferential testing to assess the risk-benefit profile of these study medications in this study population.

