11.3 Deaths, Serious Adverse Events and other Significant Adverse Events

An SAE is defined as any AE that results in any of the following outcomes:

- Major bleeding as defined by the ISTH
- AST or ALT > 10 times the upper limit of normal

Other important medical events may also be considered a SAE when, based on appropriate medical

judgement, they jeopardize the participant or require intervention to prevent one of the outcomes listed.

Study personnel will document all SAEs that occur (whether or not related to study drug). The collection period for all SAEs will begin after informed consent is obtained and end 30 days after administration of the last dose of study drug. SAEs will be graded for severity and relationship to study drug. In accordance with the standard operating procedures and policies of the local IRB, the study team will report SAEs to the IRB.

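### The SAE definition names only ISTH major bleeding and a high aminotransferase threshold, so other deaths and life-threatening events enter the SAE endpoint only by discretion

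*Protocol*

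**What the plan says.** Protocol 11.2.2 lists two outcomes that make an adverse event serious: "major bleeding as defined by ISTH, AST or ALT > 10 times the upper limit of normal". SAP 11.3 opens with "An SAE is defined as any AE that results in any of the following outcomes" and gives the same pair, starting with "Major bleeding as defined by the ISTH".

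Both documents then add a discretionary route. In the protocol it reads "Other important medical events may also be considered a SAE when, based on appropriate medical judgement, they jeopardize the participant", with a second, alternative limb for events needing intervention to avert a listed outcome.

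The protocol's safety outcome (3.3) is "Incidence of serious adverse events as defined in the study protocol". SAP 5.2.3 and SAP 11 carry SAE incidence as a safety endpoint over the study duration.

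Three other places bear on the point:

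- SAP 8.6.1 has the DSMB receive a "listing of participants with SAEs (including segregation of those involving deaths"), along with treatment-emergent AEs and discontinuations due to AEs.
- Table 2 in Protocol 11.2 has a top grade, Grade 4, described as "The participant is at risk of death due to the adverse experience as it occurred". It has no fatal grade, and nothing connects Grade 4 to seriousness.
- SAP 11.3 has deaths in its heading, but neither it nor the endpoint list in SAP 11 specifies a safety summary of deaths.

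**The concern.** A reader of an SAE table will normally assume that it contains the deaths and the life-threatening events. Under this definition it need not. A fatal or Grade 4 event involving neither major bleeding nor the aminotransferase threshold is counted only if someone chooses to count it, so two identical events may be classified differently.

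That matters for a comparison between arms. Protocol 8.2 calls the trial single-blinded without saying who is blinded. Because the capsules look identical (Protocol 8.3), the blinded party appears to be the participant. The plan does not say that whoever classifies events is unaware of treatment. Optional classification without stated blinding can distort the comparison in either direction.

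The SAE label also has uses beyond the final table. Individual reporting to the IRB (Protocol 11.2.3 and 17.2) and the DSMB's ongoing monitoring (Protocol synopsis, planned interim analyses) are both tied to SAEs, and Protocol 11.3 sets up no other real-time channel.

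**Working it through.** No figure in the plan needs reproducing; the check is of wording.

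**Step 1. Named outcomes.** Each document names two. Neither of the two is death from any cause or a life-threatening event as such. Fatal bleeding is inside the list, because Protocol 3.3 counts bleeding that contributed to death as major bleeding.

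**Step 2. The judgement clause.** It has two alternative limbs: "they jeopardize the participant or require intervention to prevent one of the outcomes listed". The second refers back to the same two outcomes and so adds little. The first is free-standing and broad enough to admit a fatal arrhythmia or a pulmonary embolism. The governing verb is permissive, however, so it never requires that they be counted.

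**Step 3. Event by event.** Events that meet neither named outcome, apart from the first row:

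| Event | Must be an SAE? | May be an SAE? | Captured elsewhere |
|---|---|---|---|
| Fatal major bleed | Yes | – | Major-bleeding outcome; efficacy |
| Death from another cause | No | Yes | Composite co-primary; time to death; ten-death trigger |
| Non-fatal pulmonary embolism | No | Yes | Exploratory thromboembolism endpoints |
| Respiratory failure with ventilation | No | Yes | Composite; ventilation endpoints |
| Severe hypotension | No | Yes | Its own safety outcome |
| Grade 4 bronchospasm or angioedema | No | Yes | AE record only |

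The last row is the least protected. Protocol 2 lists severe bronchospasm and angioedema among rare post-marketing reports for the drug, yet no endpoint is dedicated to them.

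**Step 4. Internal fit.** SAP 8.6.1 presupposes that fatal events are found among the SAEs. Steps 1 and 2 guarantee this only for deaths that involve a named outcome. The remainder of that listing depends on discretion.

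**Step 5. Illustrative scale**, for the 100 participants at which enrollment was halted (Protocol synopsis):

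- Deaths, assuming 5 to 15% mortality (not in the documents): 0.05 × 100 = 5 to 0.15 × 100 = 15.
- Mechanical ventilation, from the synopsis figure of about one-quarter of admitted patients: 0.25 × 100 = 25.
- Venous thromboembolism, from the Protocol 1 figure of up to 40%: 0.40 × 100 = up to 40.

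These show how many events could be left to judgement. They do not estimate how many were, or will be, left out of the SAE count. The categories overlap and should not be added.

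**The case against.** The strongest reply is that the definition does not stop at two outcomes. A reader might infer that other deaths and life-threatening events are not SAEs at all. The documents do not support that: the first limb of the judgement clause plainly reaches them. SAP 8.6.1 can also be read as showing that the authors expected fatal events to enter that way. This stands, and the defect is therefore optional counting, not exclusion.

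A reader might also infer that an excess of deaths in one arm could pass unseen. That is not supported either. All-cause death is the first tier of the composite co-primary endpoint (Protocol 15.3, SAP 5.2.1) and a secondary endpoint (Protocol 15.4, SAP 10.3). Ten deaths trigger interim safety review (Protocol 14, SAP 8.6.1). Hypotension, thromboembolism and ventilation have endpoints of their own, and the DSMB sees more than SAEs.

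Finally, IRB reporting follows local procedures and the DSMB works under a charter. Neither is available here, and either might require deaths to be reported regardless. The effect on oversight therefore cannot be established from these documents.

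None of this repairs the SAE endpoint itself. It still rests on optional classification, and non-fatal Grade 4 events without an endpoint of their own have no other planned comparison of life-threatening events by arm.

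**Conclusion.** The point holds for the SAE endpoint. As defined, it can omit fatal and life-threatening events, or count them unevenly between arms, and it does not fit the DSMB listing in SAP 8.6.1 or the heading of SAP 11.3. The harm is bounded: mortality is analysed separately, and several of the other serious events have their own endpoints. What is exposed is the SAE comparison and the non-fatal Grade 4 events that nothing else tabulates.

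The size cannot be fixed from the documents. The range of 5 to 15 deaths rests wholly on assumed mortality, and the share that would go unclassified is unknown. The conclusion needs neither figure; it follows from the permissive wording and the two-item list. It should be settled before an SAE comparison is reported.

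**What to change.** 1. In Protocol 11.2.2 and SAP 11.3, state that any AE that is fatal or life-threatening (Grade 4 in Protocol Table 2, SAP Table 4) is an SAE. Identify fatal events from the recorded death or AE outcome, since the severity table has no fatal grade. Keep the bleeding and aminotransferase items.
2. Reconcile SAP 8.6.1 with that definition, so that it is clear which deaths belong in the separated listing.
3. Add to SAP 11 a table of all-cause deaths and Grade 4 AEs by arm in the safety population. Show the SAE count under the current definition alongside the revised one.

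The cost is small: wording in two documents and one derived table. Deaths are recorded for the efficacy analysis, and AE severity and outcome are recorded under Protocol 9.1.12 and 11.1, so no new data collection is needed.

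The downside is a higher SAE count and some retrospective reclassification after recruitment has halted. To limit bias, reclassification should follow the recorded death and grade mechanically, without fresh judgement. Prolonged stay and lasting disability should not be added to this re-derivation, because the documents do not show that either was recorded as an attribute of an AE.

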11.3 Protocol Defined Important Medical Findings Requiring Real Time Reporting

Not applicable.

11.4 Medical Monitoring

A DSMB has been established and a DSMB charter formed. Details are noted in the Data Safety section below.

12 DISCONTINUATION AND REPLACEMENT OF PARTICIPANTS

12.1 Early Discontinuation of Study Drug

A participant may be discontinued from study treatment at any time if the participant, medical team, or the Site-Investigator feels that it is not in the participant's best interest to continue. The following is a list of possible reasons for study treatment discontinuation:

- Participant withdrawal of consent
- Participant is discharged earlier than 14 days
- Adverse event that in the opinion of the investigator would be in the best interest of the participant to discontinue study treatment
- Protocol violation requiring discontinuation of study treatment

If a participant is withdrawn from treatment due to an adverse event, the participant will be followed and treated by the study team until the abnormal parameter or symptom has resolved or stabilized.

All participants are free to withdraw from participation at any time, for any reason, specified or unspecified, and without prejudice.

The reason for the participant's withdrawal from the study will be specified in the participant's source documents. Refer to Section 10 for early termination procedures.

12.2 Withdrawal of Participants from the Study

A participant may be withdrawn from the study at any time if the participant, the medical team, or the Site-Investigator feels that it is not in the participant's best interest to continue.

All participants are free to withdraw from participation at any time, for any reason, specified or unspecified, and without prejudice.

The reason for the participant's withdrawal from the study will be specified in the participant's source documents. Refer to Section 10 for early termination procedures.

12.3 Replacement of Participants

Participants who withdraw from the study treatment will not be replaced.

Participants who withdraw from the study will not be replaced.

13 PROTOCOL VIOLATIONS

A protocol violation occurs when the participant, study coordinator or the investigator fails to adhere to significant protocol requirements affecting the inclusion, exclusion, participant safety and primary endpoint criteria. Protocol violations for this study include, but are not limited to, the following:

- Use of a prohibited concomitant medication
- Non-compliance with study drug regimen

Failure to comply with Good Clinical Practice (GCP) guidelines will also result in a protocol violation. The National Investigator in consultation with IND Sponsor will determine if a protocol violation will result in withdrawal of a participant.

When a protocol deviation occurs, a protocol deviation form detailing the deviation will be completed. A copy of the form will be filed in the study's regulatory binder.

14 DATA SAFETY MONITORING

Safety oversight will be under the direction of a Data and Safety Monitoring Board (DSMB) composed of individuals with the appropriate expertise, including clinical trials, thrombosis

expertise, clinical pharmacology, biostatistics. Members of the DSMB will be independent from the study conduct and free of conflict of interest, or measures will be in place to minimize perceived conflict of interest. The study's DSMB will review data relating to safety and efficacy, to conduct and review an interim analysis, and to ensure the continued scientific validity and merit of the study. The DSMB has been formed and includes experts in clinical trials, statistics, thrombosis, and pharmacology. A Charter has been written to guide the DSMB's activities. There will be at least two interim review(s) conducted by the DSMB for the purpose of monitoring study conduct and assessing participant safety. Study conduct will be evaluated by the DSMB when approximately 25% and 50% of participants have completed the study, or three months after initiation of enrollment (whichever comes first). When approximately 25% and 50% of participants have completed the study or 10 deaths have occurred (whichever occurs first), an interim data analysis to evaluate safety and futility will be conducted by an independent data monitoring committee. The interim analyses for efficacy will be limited to the review after 50% of participants have completed the study to limit the cost to power from multiple interim analyses.

Further details regarding the timing and content of the interim reviews is included in the statistical section below.

